#### **4.2.2. By-Study Visit Displays**

When data are collected serially over time, individual data presentations may include by-study visit displays. Visits will be presented according to the nominal visit as obtained from the CRF or laboratory data. Unscheduled visits will be included in the listings.

## 5. STATISTICAL ANALYSIS METHODS

### 5.1. General Considerations

Descriptive statistical methods will be used to summarize the data from this study. No formal hypothesis testing is planned for this trial. Unless stated otherwise, the term “descriptive statistics” refers to number of subjects (N), number of observations (n), mean, median, standard deviation (SD), Q1, Q3, minimum, and maximum for continuous data and frequencies and percentages for categorical data. Figure presentations will include appropriate variability indicator such as SD or standard error (SE).

All data collected during the study will be included in data listings. Unless otherwise noted, the data presentations will be sorted first by trial part (A or B), cohort, and subject number. Unless otherwise noted, summary tables will be separated into Part A Cohorts 1 and 2, Part A Food Effects, and Part B.

In Part A, the term “treatment sequence” refers to the sequence of treatment for each individual. “Treatment group” refers to treatment with CVL-354, at different doses, or placebo. Since Part A is a crossover study, subjects will appear in multiple groups. For Part A Cohorts 1 and 2, “Treatment period” refers to Periods 1 through 4 described in [Figure 1](#). For Part A Food Effects, “Treatment period” refers to Period 1 and 2 described in [Figure 2](#).

In Part B, “treatment group” refers to treatment with CVL-354, at different doses, or placebo QD or BID. Doses will be determined based on data from Part A.

For summary presentations, placebo subjects will be combined across cohorts within a given Part.

The statistical analyses will be conducted with the SAS® software package Version 9.4 or higher.

### 5.2. Populations for Analyses

The analysis sets that are defined for this trial are described in [Table 3](#).

**Table 3: Analysis Set Descriptions**

Term	Description
All Screened	All participants who consent to participate in the clinical trial
Randomized	All participants who are randomized to IMP
Safety Analysis Set	All randomized participants who receive at least 1 dose of IMP
PK Analysis Set	All participants in the Safety Analysis Set who have at least 1 quantifiable CVL-354 concentration

Abbreviations: IMP=investigational medicinal product; PK=pharmacokinetic.

### 5.3. Statistical Hypotheses

No formal hypothesis testing is planned for this trial.

## 5.4. Multiplicity Adjustment

All analyses will be conducted without adjustment for multiple comparisons.

## 5.5. Strata and Covariates

No strata or covariates will be examined.

## 5.6. Subject Disposition, Demographic and Baseline Characteristics

Subject disposition will be presented for all screened subjects. The number of subjects who were screened, met all eligibility criteria, as well as the number of subjects included in different Analysis sets will be presented. Screen failures and reason for failure will be presented. The number of subjects who completed the study and discontinued from the study will be provided, as well as reason for discontinuation. Additionally, the number of days on study will be summarized. Data will be presented by cohort for Part A Cohorts 1 and 2, sequence for Part A Food Effects, and treatment group for Part B. For Part A Cohorts 1 and 2, a separate presentation by sequence will be provided.

Demographic data and baseline characteristics including age, sex, childbearing potential, ethnicity, height, weight, body mass index (BMI) will be summarized using descriptive statistics with respect to randomized population. Data will be presented by cohort for Part A Cohorts 1 and 2, sequence for Part A Food Effects, and treatment group for Part B. For Part A Cohorts 1 and 2, a separate presentation by dose will be provided.

## 5.7. Exposure to Treatment

The number of subjects who received IMP, including dose, and the number of subjects who completed dosing through the last visit/date will be summarized. Reason for premature discontinuation of IMP will be summarized. Additionally, for Part B, the duration of exposure to IMP will be summarized.

A black and white image showing a series of horizontal bars of varying lengths and positions, suggesting a redacted document. The bars are composed of black pixels on a white background. There are several short bars on the left side, and a long bar spanning most of the width of the image. The bars are irregular in shape, with some having sharp ends and others being more rounded.

## 5.9. Safety Analysis

All safety analyses will be performed on the Safety Analysis Set. Should any subjects receive a treatment other than their randomized treatment, the treatment received will be used in the safety presentation. All analyses will be presented separately by Part. Analyses will be presented by treatment group. For Part A, treatments will be assigned as described in [Section 4.2.1](#).

### 5.9.1. Adverse Events

Adverse events will be mapped to a Medical Dictionary for Regulatory Activities (MedDRA) version 25.1 or later by system organ class, preferred term, and severity. If a subject experiences multiple events that map to a single preferred term, the greatest Common Terminology Criteria for Adverse Events (CTCAE) toxicity grade and strongest investigator assessment of relation to IMP will be assigned to the preferred term for the appropriate summaries. Events with missing severity or relationship, will be classified as outlined in [Section 4.1.1.1](#).

For Part A, all TEAEs will be attributed to a treatment period based on start date as specified in [Section 4.2.1](#). Any TEAE occurring during the washout period will be attributed to the treatment most recently administered.

The occurrence of TEAEs will be summarized by treatment group for Part A and Part B, using preferred terms, system organ class, and severity. Separate summaries of TEAEs, treatment-emergent serious adverse events (TESAEs), TEAEs by severity, TEAEs related to IMP, AESIs, and events leading to the discontinuation of study will be generated by system organ class and preferred terms. For Part B, a separate analysis of AEs leading to the discontinuation of IMP will be provided.

All AEs reported will be listed for individual subjects showing both verbatim and preferred terms and treatment group at onset of the AE. All AEs that occurred prior to the initiation of IMP will be excluded from the tables but will be included in the listings.

Missing onset dates will be imputed as previously outlined in [Section 4.1.1.2](#) as required to determine treatment-emergent events.

### 5.9.2. COVID-19 Coronavirus Infection Testing

Participants must have COVID-19 testing done with a negative test result within a maximum of 5 days prior to, but as close as possible to each admission to the clinic. COVID-19 testing may be performed after admission per the investigator's discretion. An AE will be recorded if the result is positive or indeterminate. Indeterminate tests will be repeated. COVID-19 testing results will be listed.

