Confidential Page 26 of 96 Version 3.0: 25 May 2022

^{-5;} ECG=electrocardiogram;

ET=early termination; FSH=follicle stimulating-hormone; IMP=investigational medicinal product; PK=pharmacokinetic;

a Contact with participant via phone call, internet/web, or other acceptable means of communication to check on their status 14±3 days after their final dose of IMP in the trial.

- b Participants must have COVID-19 testing done with a negative test result within a maximum of 5 days prior to, but as close as possible to, each admission to the clinic. COVID-19 testing may be performed after admission per the investigator's discretion.
- c Assessments can be completed at Check-in for all participants in the cohort (sentinel and non-sentinel) during each period. No additional Check-in assessments are required for non-sentinel participants provided that those participants remain domiciled under close observation and the Check-in assessments are performed within 48 hours prior to dosing.
- ^d There will be a washout period of at least 5 days between doses.
- ^e Predose assessments to be completed within 60 minutes of dosing unless otherwise noted.
- f Inclusion/exclusion criteria will be assessed at the start of each trial period to ensure ongoing participant eligibility with the exception of age or assessments that are only scheduled during Screening (eg, height).
- g Medical occurrences that begin before the start of IMP dosing but after obtaining informed consent will be recorded as medical and/or psychiatric history. This also applies to replacement participants.
- h An alcohol test (breathalyzer or blood/urine) is required at Screening and at Check-in for each period. The alcohol test may be conducted at any time during the trial at the discretion of the investigator.
- i Period 1 only.
- ^j Full physical and neurological examinations should be completed at Screening and Check-out of each period (or ET). A limited examination (cardiovascular, pulmonary, and gastrointestinal) should be completed at Check-in to clinic on Day -1 of each period. Symptom driven physical and/or neurological examinations may be done at any time point during the trial at the investigator's discretion.
- ^k A one-time baseline report of continuous ECG telemetry will be recorded for each participant by the site for a minimum of 12 hours starting on Day -1 prior to first dose. This baseline report will also be required for replacement participants.

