8.4.1. Time Period and Frequency for Collecting AE and SAE Information

All AEs and SAEs will be recorded from the first dose of IMP until follow-up contact at the time points specified in the Schedules of Assessments (Section 1.3).

Medical occurrences that begin before the start of IMP dosing but after obtaining informed consent will be recorded as medical and/or psychiatric history.

All SAEs will be recorded and reported to the medical monitor immediately and under no circumstance should this exceed 24 hours, as indicated in Section 10.3 (Appendix 3). The investigator will submit any updated SAE data to the medical monitor within 24 hours of it being available.

Investigators are not obligated to actively seek AE or SAE after conclusion of the trial participation. However, if the investigator learns of any SAE, including a death, at any time after a participant has been discharged from the trial, and he/she considers the event to be related to the IMP or trial participation, the investigator must promptly notify the sponsor.

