10.3.1. Definition of AE

Table 13: Definition of AE

AE Definition

- An AE is any untoward medical occurrence in a patient or clinical trial participant, temporally associated
 with the use of trial treatment, whether or not considered related to the trial treatment.
- NOTE: Signs and symptoms and/or abnormal laboratory test result indicating a common underlying pathology/diagnosis should be reported as a single adverse event.

Table 14: Events Meeting the AE Definition

Events Meeting the AE Definition

- Any abnormal laboratory test results (hematology, clinical chemistry, or urinalysis) or other safety
 assessments (eg, ECG, radiological scans, vital sign measurements), including those that worsen from
 baseline, considered clinically significant in the medical and scientific judgment of the investigator.
- Exacerbation of a chronic or intermittent pre-existing condition including either an increase in frequency and/or intensity of the condition.
- New conditions detected or diagnosed after trial treatment administration even though it may have been
 present before the start of the trial.
- Signs, symptoms, or the clinical manifestations of a suspected drug-drug interaction.
- Signs, symptoms, or the clinical manifestations of a suspected overdose of either trial treatment or a concomitant medication.

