### **Treatment-emergent Adverse Event (TEAE)**

Any event reported on the eCRF that occurs on or after the initiation of IMP and up to the final follow-up contact is considered treatment-emergent. Additionally, it is assumed that an Adverse Event which was reported to have started on Day 1 without an associated onset time may have occurred after the initiation of IMP. Hence, Adverse Events occurring on Day 1 with no associated onset time are assumed to be treatment-emergent.

For Part A, treatment-emergent adverse events will be attributed to a period based on the start date. An adverse event starting on or after the initiation of IMP in Period 1 and before dosing with IMP for Period 2, or through follow-up contact if subject discontinues prior to Period 2, is considered a Period 1 TEAE. For Cohort 1 and 2, an adverse event starting on or after the initiation of IMP in Period 2 and before dosing with IMP for Period 3, or through follow-up contact if subject discontinues prior to Period 3 is considered a Period 2 TEAE. An adverse event starting on or after the initiation of IMP in Period 3 and before dosing with IMP for Period 4, or through follow-up contact if subject discontinues prior to Period 4, is considered a Period 3

TEAE. An adverse event occurring after dosing for Period 4, through follow-up contact, is considered a Period 4 TEAE.

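### SAP 5.9.2 calls for an AE at an indeterminate COVID-19 test before the repeat is known; after first dose, a negative repeat would still leave a TEAE under the preceding treatment

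*SAP*

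**What the plan says.** SAP 5.9.2 sets the COVID-19 rule: "An AE will be recorded if the result is positive or indeterminate. Indeterminate tests will be repeated". It adds that test results will be listed. It does not make the AE depend on the repeat.

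The protocol's COVID-19 text (section 1.3 footnotes and section 10.2) covers when to test and contains no AE rule. Its general rule for abnormal laboratory results and other safety assessments, in section 10.3.1, counts them as AEs when "considered clinically significant in the medical and scientific judgment of the investigator". SARS-CoV2 testing appears in the safety laboratory table of section 10.2.

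On timing, protocol 8.4.1 says "All AEs and SAEs will be recorded from the first dose of IMP until follow-up contact", and for anything earlier: "Medical occurrences that begin before the start of IMP dosing but after obtaining informed consent will be recorded as medical and/or psychiatric history".

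On analysis, SAP 4.1.2 defines treatment emergence by time alone: "Any event reported on the eCRF that occurs on or after the initiation of IMP and up to the final follow-up contact is considered treatment-emergent". SAP 5.9.1 adds, for Part A, "Any TEAE occurring during the washout period will be attributed to the treatment most recently administered", and for events before dosing, "All AEs that occurred prior to the initiation of IMP will be excluded from the tables but will be included in the listings".

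**The concern.** TEAEs are a primary endpoint in both parts. An inconclusive assay followed by a negative repeat is hard to describe as an untoward medical occurrence, which is how both documents define an AE. Read literally, the SAP nevertheless has it recorded as an AE. If it falls after first dose, the time-based TEAE definition then carries it into the tables. Active dose groups in the single-dose part have six participants, so one such record is visible in a primary safety table. The SAP states that it is based on protocol Version 3.0, so a recording rule that the protocol lacks, and that conflicts with the protocol's AE definition, should be reconciled.

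**Working it through.** The plan gives no figure on this point, so there is nothing to reproduce. The check follows the rules and then counts the tests that they can affect.

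**Rules in sequence**

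1. Indeterminate result: SAP 5.9.2 calls for an AE at once. Protocol 10.3.1 would first ask whether the investigator finds it clinically significant.
2. Repeat negative: neither document says what happens to the AE.
3. Result before first dose: medical history under protocol 8.4.1. If entered as an AE anyway, SAP 5.9.1 keeps it out of the tables and lists it.
4. Result on or after first dose: a TEAE under SAP 4.1.2. In Part A it is assigned to the treatment most recently given.

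**Which tests fall after first dose**

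Inputs: about 16 participants in Cohorts 1 and 2, 8 in Cohort 3 and 50 in Part B (protocol 1.1). Cohorts 1 and 2 check in and out in each of four periods (protocol 1.2) and are tested "prior to, but as close as possible to, each admission to the clinic". Cohort 3 stays in the clinic across both periods (protocol 4.1.1.2) and Part B has one admission, so their required test precedes first dose. I assume full enrolment, one mandated test per admission and no replacements.

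- All mandated tests: 16 × 4 + 8 + 50 = 122.
- After first dose: 16 × 3 = 48, and 48/122 = 39%.
- Before first dose: 16 + 8 + 50 = 74, and 74/122 = 61%.

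**Split by preceding treatment**

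Each period has 6 active and 2 placebo participants per cohort (3:1 of 8, protocol 4.1.1.1). The exposed intervals follow Periods 1, 2 and 3.

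- After active drug: 2 cohorts × 3 periods × 6 = 36.
- After placebo: 2 × 3 × 2 = 12.
- No mandated test follows the Period 4 dose.

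**How one record would appear**

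- Active single-dose level: 1/6 = 17%.
- Placebo pooled over the two cohorts (SAP 5.1; each participant has one placebo period, so 16): 1/16 = 6%.

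**Illustration only**

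The documents give no indeterminate rate. For an assumed rate p, with independent tests, the chance of at least one indeterminate result among the 48 is 1 − (1 − p)^48:

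| Assumed p | Expected number (48p) | Chance of at least one |
|---|---|---|
| 0.5% | 0.24 | 21% |
| 1% | 0.48 | 38% |
| 2% | 0.96 | 62% |
| 5% | 2.4 | 91% |

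**The case against.** The strongest reply is that the SAP does not govern AE recording. The investigator records AEs under the protocol, and the only COVID-19 analysis in SAP 5.9.2 is a listing. Protocol Version 3.0 reports that dose escalation in Cohorts 1 and 2 was already complete, and the SAP is based on that version. The 48 tests therefore very probably preceded this SAP sentence, and any AEs from them were or were not entered under site procedures that are not in these documents. This stands. It means that the table of assumed rates is not a forecast, and the actual number may be zero. It does not remove the conflict in the text, or the lack of a rule for any such AE already in the database.

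A second reply is that over-inclusive counting fits the SAP's other conservative conventions, such as imputing a missing severity as Grade 3, and that dropping recorded AEs by rule could override an investigator who judged the result clinically significant. The second half of this stands, and the fix has to respect that judgement.

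A third is that the automatic AE for a positive result also bypasses the clinical-significance test. That is true of the wording, but protocol 10.3.1 separately lists newly diagnosed conditions as AEs, and a confirmed infection can fall there. An inconclusive assay is not a diagnosis.

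Three stronger readings are tempting, and the documents do not support them:

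- A reader might infer that every indeterminate test with a negative repeat becomes a TEAE. The 74 pre-dose tests cannot. Cohort 3 and Part B are exposed only through discretionary tests after dosing, whose number is unknown.
- A reader might infer that the event is held against the drug. Assignment to a treatment group is tabulation, and that group may be placebo. Causality is the investigator's assessment, and SAP 4.1.1.1 imputes a relationship only when the assessment is missing.
- A reader might infer that all pre-dose results distort the safety tables. SAP 5.9.1 excludes them. For those tests the mismatch is only between an AE entry and medical history.

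**Conclusion.** The point holds in a limited form. SAP 5.9.2 conflicts with protocol 10.3.1 by making an indeterminate result an AE before its repeat. For tests after first dose, the SAP's own definitions would then tabulate a result that repeats negative as a TEAE of the preceding treatment. The reach is 48 mandated tests in Part A Cohorts 1 and 2, given full enrolment and completion, plus any discretionary tests after dosing. Each affected record would weigh 1/6 at an active dose level or 1/16 on pooled placebo. Whether any exists cannot be told from the documents, but the sponsor can count them. This is a minor matter of definition and presentation that is worth settling because the correction is nearly free.

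**What to change.** In SAP 5.9.2, delete the reference to indeterminate results from the sentence that triggers an AE, and align the section with protocol 8.4.1 and 10.3.1:

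- Classify an indeterminate result only after its repeat, and keep it in the COVID-19 listing in every case.
- Count it as a TEAE only if it starts on or after first dose and either the repeat is positive or the investigator judges the result clinically significant.
- State how a missing repeat, or one that is again indeterminate, is handled.
- Keep any AE already entered solely for an indeterminate test with a negative repeat in the AE listing, and identify it by a footnote so that TEAE counts can be read with and without it. Cross-refer to the TEAE definition in SAP 4.1.2, which otherwise counts every event on the eCRF.

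The cost is one SAP sentence and a footnote. No recorded data change.

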### 5.9.3. Concomitant Medications and Non-Drug Therapy/Procedures

Prior and concomitant medications will be coded using the World Health Organization (WHO) Drug dictionary (Version: Global B3, March 2021 or later). Concomitant medications will be summarized by frequency of classification and preferred term and presented by treatment group.

Prior and concomitant non-drug therapy/procedures will be coded using MedDRA Version 24.0 or higher. Concomitant non-drug therapy/procedures will be summarized by frequency of system organ class and preferred term and presented by treatment group.

#### 5.9.4. Clinical Laboratory Assessments

Descriptive summaries of selected (quantitative) clinical laboratory results will be presented by study day and treatment group. Laboratory values outside the normal range for each parameter will be identified using shift tables. Each subject's hematology, blood chemistry, and quantitative urinalysis values will be flagged as "low" (below the lower limit of normal/LLN), "normal" (within the normal range), or "high" (above the upper limit of normal/ULN) relative to the normal ranges of the central laboratory. Each subject's qualitative urinalysis values will be flagged as "normal" or "abnormal". Shifts from baseline, or period baseline if Part A, to high/normal/low status for hematology and blood chemistry parameters that are not CTCAE graded will be presented to the maximum post-baseline/post-period baseline value and the minimum post-baseline/post-period baseline value for each laboratory test. Shifts from baseline, or period baseline if Part A, to normal/abnormal status for urinalysis parameters that are not CTCAE graded will be presented to the maximum post-baseline/post-period baseline value and the minimum post-baseline/post-period baseline value for each laboratory test. Otherwise, for hematology, blood chemistry, and urinalysis parameters that are CTCAE graded, laboratory toxicities will be programmatically graded by severity using Cerevel's modified CTCAE Version 5.0. Shifts from baseline, or period baseline if Part A, to greatest (worst) treatment-emergent laboratory toxicity will be presented.

The number and percentage of subjects who have post-baseline/post-period baseline elevations in liver transaminase (alanine aminotransferase [ALT] or aspartate aminotransferase [AST]) or bilirubin abnormalities in relation to fold above the ULN will be summarized according to the Food and Drug Administration's Premarketing Clinical Evaluation on Drug-Induced Liver Injury Guidance for Industry ([FDA, 2009](#)). Abnormal hepatic laboratory values will be categorized and evaluated for any occurrence among all post-baseline/post-period baseline assessments (where "and" in the bulleted list below indicates elevations occurring at the same visit). Within each laboratory parameter grouping, a subject may be counted once per elevation criteria using the worst-case result. That is, a subject with a worst case ALT elevation  $>3 \times$  ULN would be counted once in the  $ALT >1.5 \times$  ULN category and once in the  $ALT >3 \times$  ULN category, regardless of how many ALT elevations the subject had that met the  $>3 \times$  ULN and  $>1.5 \times$  ULN elevation criteria.

- ALT and/or AST  $>3 \times$  ULN and total bilirubin  $>1.5$  or  $2 \times$  ULN
- AST  $>1.5, 3, 5, 10, 20 \times$  ULN
- ALT  $>1.5, 3, 5, 10, 20 \times$  ULN
- Total bilirubin  $>1, 1.5, 2 \times$  ULN
- Alkaline phosphatase (ALP)  $>1.5 \times$  ULN

In addition, a Hy's law plot, a shift plot showing liver safety panel tests over time (baseline/period baseline vs. post-baseline/post-period baseline), and distribution plots of ALT, AST, ALP, and bilirubin over time will be produced. The plots to be included are the scatter plot

of maximum transaminase versus maximum bilirubin, the liver test safety panel over time and the distribution of ALT by time and treatment. The distribution plots for AST, ALP, and bilirubin will use the same format as is used for ALT.

